7.0 RECRUITMENT PLAN

All eligible patients, regardless of race, will be approached for participation. No additional measures, e.g. advertisement, payment to patients, will be employed to recruit patients.

During the initial conversation between the investigator/research staff and the patient, the patient may be asked to provide certain health information that is necessary to the recruitment and enrollment process. The investigator/research staff may also review portions of their medical records at MSKCC in order to further assess eligibility. They will use the information provided by the patient and/or medical record to confirm that the patient is eligible and to contact the patient regarding study enrollment. If the patient turns out to be ineligible for the research study, the research staff will destroy all information collected on the patient during the initial conversation and medical records review.

Participation in the study is completely voluntary. Patients/LAR will be required to read, agree to, and sign an IRB-approved informed consent form prior to registration on this trial. Patients will not receive payment for their participation on this study. Patients are free to withdraw from the study without consequence at any time.

Potential research subjects will be identified by a member of the patient's treatment team, the protocol investigator, or research team at Memorial Sloan-Kettering Cancer Center (MSKCC). If the investigator is a member of the treatment team, s/he will screen their patient's medical records for suitable research study participants and discuss the study and their potential for enrolling in the research study. Potential subjects contacted by their treating physician will be referred to the investigator/research staff of the study.

Assignment of Patient Number

Patient numbers are assigned in sequential order as patients patient enrolls onto study.

The Investigator will certify that the patient satisfies all eligibility criteria at screening and continues to satisfy all inclusion and exclusion criteria on Cycle 1, Day 1 prior to dosing.

Memorial Sloan Kettering Cancer Center
[name]
[name]

Enrolled Patient Definition

Patients who have consented to the study and have received at least one dose of study treatment will be considered enrolled and evaluable. Those patients who've consented but did not successfully complete the screening process and did not receive a dose of ZW25 will be considered a screen failure. Patient numbers for patients who screen fail will not be re-issued.

7.1 Research Participant Registration

Confirm eligibility as defined in the section entitled Inclusion/Exclusion Criteria. Obtain informed consent, by following procedures defined in section entitled Informed Consent Procedures. During the registration process registering individuals will be required to complete a protocol specific Eligibility Checklist. The individual signing the Eligibility Checklist is confirming whether the participant is eligible to enroll in the study. Study staff are responsible for ensuring that all institutional requirements necessary to enroll a participant to the study have been completed. See related Clinical Research Policy and Procedure #401 (Protocol Participant Registration).

8.0 INFORMED CONSENT PROCEDURES

Before protocol-specified procedures are carried out, consenting professionals will explain full details of the protocol and study procedures as well as the risks involved to participants prior to their inclusion in the study. Participants will also be informed that they are free to withdraw from the study at any time. All participants or their LARs must sign an IRB/PB-approved consent form indicating their consent to participate. This consent form meets the requirements of the Code of Federal Regulations and the Institutional Review Board/Privacy Board of this Center. The consent form will include the following:

1. The nature and objectives, potential risks and benefits of the intended study.
2. The length of study and the likely follow-up required.
3. Alternatives to the proposed study. (This will include available standard and investigational therapies. In addition, patients will be offered an option of supportive care for therapeutic studies.)
4. The name of the investigator(s) responsible for the protocol.
5. The right of the participant to accept or refuse study interventions/interactions and to withdraw from participation at any time.

Before any protocol-specific procedures can be carried out, the consenting professional will fully explain the aspects of patient privacy concerning research specific information. In addition to signing the IRB Informed Consent, all patients must agree to the Research Authorization component of the informed consent form.

Memorial Sloan Kettering Cancer Center
[name]
[name]

Each participant or their LAR and consenting professional will sign the consent form.
The participant must receive a copy of the signed informed consent form.

9.0 PRE-TREATMENT/INTERVENTION

Screening Visit

In some cases, clinical assessments performed prior to obtaining informed consent may be used to qualify the patient for the study. These include radiological tumor assessment, physical examinations, hematology, serum chemistry results, coagulation studies, urinalysis, or other assessments which may be considered part of normal standard of care. In these cases, repeat assessments may not be necessary prior to enrollment, unless individual parameters require further study or confirmation and are clinically appropriate.

Within 28 days prior to treatment start:

- Written informed consent
- History and Physical examination
- Review of concomitant medications
- Vital signs (blood pressure, heart rate and temperature), weight and height
- ECOG Performance status
- Toxicity assessment
- 12-lead ECG
- Echocardiogram
- Radiographic tumor measurements (CT C/A/P, MRI)
- Screening Biopsy (3 Cores) if deemed safe and feasible (Refer to: Exploratory Correlative Studies section for details)
- Patients must have documented HER2 overexpression, defined as 3+ by IHC or 2+ with gene amplification by FISH (HER2/CEP17 ratio ≥ 2) or HER2 amplified (fold change ≥ 2) on MSK IMPACT any time prior to starting treatment
- Hepatitis B Testing, if not done previously at MSK to rule out active infection (see exclusion criteria for details)

Within 14 days prior to treatment start:

- Complete Blood Count (CBC) with differential
- Comprehensive profile (BUN, creatinine, sodium, potassium, chloride, CO2, calcium, glucose, total bilirubin, total protein, albumin, alkaline phosphatase, AST, ALT)
- Coagulation tests: Prothrombin time, APTT and INR (PT/PTT)
- Magnesium
- Uric Acid
- Urinalysis
- Pregnancy test (in women of childbearing potential)
 - Women of child bearing potential (WCBP), defined as a sexually mature woman who has not undergone surgical sterilization or who has not been naturally postmenopausal for at least 12 consecutive months (i.e., who has had menses any time in the preceding 12 consecutive months) must agree to use effective

contraceptive methods. Acceptable single methods include intrauterine device, vasectomy of a female patient's male partner, and contraceptive rod implanted into the skin. Abstinence (relative to heterosexual activity) can be used as the sole method of contraception if it is consistently employed as the patient's preferred and usual lifestyle and if considered acceptable by local regulatory agencies and ERCs/IRBs. Periodic abstinence (e.g., ca, ovulation, sympto-thermal, post-ovulation methods, etc.) and withdrawal are not acceptable methods of contraception. Acceptable combination methods (requiring use of two of the following) are acceptable: diaphragm with spermicide (cannot be used in conjunction with cervical cap/spermicide), cervical cap with spermicide (nulliparous women only), contraceptive sponge (nulliparous women only), male condom or female condom (cannot be used together), or hormonal contraceptive such as oral contraceptive pill, estrogen/progestin pill or progestin-only pill), contraceptive skin patch, vaginal contraceptive ring, or subcutaneous contraceptive injection. Acceptable methods of contraception must be used while on study treatment and for at least twelve weeks after the last dose of ZW25.

- All female patients of child-bearing potential will complete a serum beta-human chorionic gonadotropin (β -hCG) or urine pregnancy test (not more than 3 days before the first dose of ZW25); this test must be negative for the patient to be enrolled and to receive the study drug.

ECGs are required during screening, on Cycle 1 Day 1 and Cycle 3 Day 1. Vital signs will be evaluated according to the Schedule of Assessments listed on section 11 of the protocol.

10.0 TREATMENT/INTERVENTION PLAN

Study treatment will begin on Day 1 of each 4 week dosing cycle (28 days).

In this study the recommended ZW25 dose will be 20mg/kg intravenously (IV) every two weeks on Days 1 and Days 15 a 28-day cycle.

Patients will continue to receive study treatment until they present with progressive disease (PD) per Response Evaluation Criteria in Solid Tumors (RECIST) version 1.1, develop unacceptable toxicity or withdraw consent, whichever comes first, or until the study is terminated.

Tumor assessments, including radiological assessments by computerized tomography (CT) or magnetic resonance imaging (MRI) scans are performed at Screening and subsequently every eight weeks for the first 24 weeks and then every twelve weeks until progression of disease, death or initiation of subsequent anti-cancer therapy, whichever occurs first.

Pre- and post-treatment fresh tumor biopsies, blood and serum samples will be collected for biomarker analysis. Post-treatment tumor biopsy will only be performed upon

Memorial Sloan Kettering Cancer Center
[name]
[name]

progression of disease. Results from tissue testing will not be returned to patients. (See Exploratory Correlative Studies section for details)

End of Treatment and Follow-up

End of Treatment Visit

Patients may voluntarily withdraw from the study treatment at any time for any reason, and without prejudice to further treatment. In addition, patients may be withdrawn by the Investigator if they do not feel the patient is deriving clinical benefit or because the patient is experiencing unacceptable toxicity. The reasons for which a patient may be removed from study are listed in Section 12.

Patients who withdraw or is removed from study treatment will have an end of treatment visit within 7 days of the decision to discontinue study treatment. Additionally, these patients will undergo a 30-day follow-up safety visit. The eCRF will capture reasons for withdrawal.

30-Day Safety Follow-up

A safety follow-up visit will occur 30 days (+14 days) after the last treatment.

All serious adverse events, and those adverse events assessed by the Investigator as at least possibly related to study drug should continue to be followed until they resolve or stabilize, whichever comes first. Reporting of SAEs are detailed in Section 15.1.

Survival Follow-up

All patients who discontinue study treatment for any reason will be proceed onto survival follow up. Patients will be followed up for survival status every 3 months (from End of treatment visit) for 2 years until death, lost to follow up or withdrawal of consent.

Exploratory Correlative Studies

1. Anti-drug antibodies (ADA) will be assessed at baseline (baseline ADA can be collected on C1D1 pre dose) and pre-dose at Cycles 2, 4, 6, 8, 12, 18, 24 Day 1. The immunogenicity testing will be performed using validated assays in 3 steps as follows: screening assay (Tier 1), confirmation assay (Tier 2), and titration (Tier 3). Only samples positive in the screening assay will be tested in confirmation and further titrated to determine the titer of ADA.

At each timepoint, 5mL of blood will be collected into a red top tube and processed as follows:

- Invert 5x
- Clot at least for 30 minutes
- Separate serum within 30-60 minutes of collection
- Centrifuge 1000-2000 x g at 4c for 15-20min
- ~1.25mL serum into each 2mL cryovial

Storage: Store at -70° F/-80° F (storage at -20° F acceptable) for up to 1 month. Ship frozen on dry ice monthly. Blood samples for ADA will be processed and stored at the Immune Monitoring Facility (IMF) until batch shipment to Zymeworks, Inc.

Memorial Sloan Kettering Cancer Center
[name]
[name]

2. To explore the molecular associations between the *HER2* biomarkers: gene amplification (by NGS and ISH), protein overexpression by immunohistochemistry (IHC) and mutational status and/or copy # variations of relevant cancer-related genes using MSK-IMPACT platform in all patients and to determine mechanisms of underlying response and resistance.
3. Mandatory pre-treatment and post-treatment tumor biopsies will be obtained on all patients to assess *HER2* expression, its association with treatment response and other genetic changes over time. Attempts will be made to collect 3 cores (Flash Frozen) of tumor material at each time point for research purposes under the current study. Biopsies will only be performed if deemed safe and feasible by the investigator. Post-treatment biopsy will only be done upon progression of disease. Tissue testing will be performed in the CMO. To determine mutational status and/or copy number variations of relevant cancer related genes using MSK-IMPACT platform in patients with response to therapy. MSK-IMPACT tests will be done on new biopsy specimens for research purposes in the context of this protocol. Results from these testing will not be reported to patients.
4. To determine the ability of the laboratory parameters to predict clinical benefit:
 - a. All patients will undergo mandatory pre-treatment fresh tumor biopsy (if deemed clinically safe). Post-treatment fresh tumor biopsy will be done upon disease progression.
5. To evaluate the predictive value of changes in circulating tumor DNA variant allele frequency during treatment for response to ZW25. Circulating plasma cell-free DNA will be collected at pre-treatment (any time prior to C1D1), and at End of Treatment. MSK's standard cfDNA workflow will be followed (one streck tube).
 - a. Liquid biopsy through the sequencing of plasma ctDNA has the potential to address multiple biologic questions, including global tumor heterogeneity. Targeted deep sequencing of candidate driver oncogenes facilitates analysis of the clonal structure of the tumor, and prioritization of clinically relevant actionable targets. As blood content theoretically integrates mutational data from all sites of disease, deep analysis of plasma ctDNA may offer a solution to the problem of assessing intratumoral heterogeneity with tumor biopsies, and ultimately could define a systemic genomic approach to guide application of targeted therapies. A novel bioinformatics algorithm called FACETS developed at Memorial Sloan Kettering will be applied to interrogate clonality from targeted sequencing of ctDNA.

Whole genome or whole exome sequencing will not be done in this study unless activity is seen after data review, at which point the protocol may be amended to include additional objectives.

Incidental Inherited Genomic Findings:

In the course of this research it is possible that some patients whose tumors are analyzed through investigational "next-generation" profiling in a research (non-CLIA) environment will be found to have somatic or germline mutations in genes that are known to be associated with an increased risk of cancer or other diseases. It will be stated in the consent that the participants will not receive any specific results from

Memorial Sloan Kettering Cancer Center
[name]
[name]

research tests. The consent will tell participants that if they wish to have genetic testing done for personal reasons than they should make an appointment with the MSK Clinical Genetics Service.

If in the course of this research a research finding is obtained that, in the opinion of the investigator, may be critical to the preventive care of the participant or their family, the investigator can communicate that finding to the IRB Genomic Advisory Panel (GAP). The finding will be reviewed by the GAP to determine whether the incidental finding should be discussed with the participant. For MSK, in the event that the GAP determines that the finding should be discussed with the participant, and the participant has consented to be re-contacted, then the treating/consenting physician shall be contacted by the panel and asked to refer the participant to the Clinical Genetics Service for further discussion of the research finding.

The following information must be provided to GAP for review:

- Participant Name/MRN #
- Type of Biospecimen (tissue, blood, saliva)
- Incidental Finding
- Collection Protocol #
- Contact: [contact]

6. Early changes in clonal variant allele frequency of *HER2* may serve as a powerful predictor of response to targeted therapy. We hypothesize that plasma ctDNA can be used as a non-invasive early predictive biomarker to distinguish between responders and non-responders to targeted therapy, refining precision medicine. Clonal changes of actionable drivers and the emergence of new somatic genetic alterations through serial ctDNA sequencing should offer novel insights into understanding and overcoming drug resistance driven by Darwinian clonal evolution. This may be paradigm changing in the way we select therapy to treat patients and fundamentally change future clinical trials design.
7. To examine ORR in each cohort by different types of molecular alterations, *HER2* amplification (by NGS and ISH separately), mutation and *HER2* overexpression, and assess their predictive value for response.

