2.0 OBJECTIVES AND SCIENTIFIC AIMS

Primary Objective:

- To determine Overall Response Rate [ORR = Complete Response (CR) + Partial Response (PR)] by RECIST v 1.1 ≤ 24 weeks from the start of treatment

Secondary Objectives:

- To determine Progression Free Survival (PFS) rate at 24 weeks
- To determine Clinical Benefit Rate (CBR) by 24 weeks
- To determine PFS and Overall Survival (OS)
- To determine Duration of Response (DOR)
- To determine the rate of Serious Adverse Events (SAE) of ZW25 by Common Terminology Criteria for Adverse Events version 5 (CTCAE v 5.0)

Exploratory Objectives:

1. Anti-drug antibodies (ADA) will be assessed at baseline (baseline ADA can be collected on C1D1 pre dose) and pre-dose at Cycles 2, 4, 6, 8, 12, 18, 24 Day 1. The immunogenicity testing will be performed using validated assays in 3 steps as follows: screening assay (Tier 1), confirmation assay (Tier 2), and titration (Tier 3). Only samples positive in the screening assay will be tested in confirmation and further titrated to determine the titer of ADA.
2. To explore the molecular associations between the *HER2* biomarkers: gene amplification (by Next Generation Sequencing [NGS] and in situ Hybridization [ISH]), protein overexpression by immunohistochemistry (IHC) and mutational status and/or copy # variations of relevant cancer-related genes using MSK-IMPACT platform in all patients with new research biopsies collected under this protocol, and to determine mechanisms of underlying response and resistance. Mandatory pre-treatment and post-treatment (collected upon progression of disease) tumor biopsies will be obtained on all patients for this purpose. Tissue testing will be performed in the Center for Molecular Oncology.
3. To examine ORR in each cohort by different types of molecular alterations, *HER2* amplification (by NGS and ISH separately), mutation and *HER2* overexpression, and assess genomic changes with response for potential predictive signatures.
4. To evaluate the predictive value of changes in circulating tumor DNA variant allele frequency during treatment for response to ZW25.

Memorial Sloan Kettering Cancer Center
[name]
[name]

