
6.0 CRITERIA FOR PARTICIPANT ELIGIBILITY

6.1 Participant Inclusion Criteria

1. Patients must be enrolled or agree to consent to the companion genomic profiling study MSKCC IRB# 12-245 Part A. Results are not required prior to

Memorial Sloan Kettering Cancer Center
[name]
[name]

initiating treatment on protocol, unless patients do not have other test results by IHC or FISH confirming HER2 overexpression.

2. Patients must have recurrent or persistent HER2 overexpressing endometrial cancer or endometrial carcinosarcoma. HER2 overexpression is defined as 3+ by IHC or 2+ with gene amplification by FISH (HER2/CEP17 ratio ≥ 2) or HER2 amplified (fold change ≥ 2) on MSK IMPACT.
3. Histologic documentation of diagnosis of endometrial carcinoma or carcinosarcoma is required.
4. Age ≥ 18 years
5. Patients must have had at least one but no more than two prior chemotherapeutic regimens for management of endometrial carcinoma (including neo-adjuvant and/or adjuvant chemotherapy). Initial treatment may include chemotherapy, chemotherapy and radiation therapy, and/or consolidation/maintenance therapy. Chemotherapy administered in conjunction with primary radiation as a radio-sensitizer WILL be counted as a systemic chemotherapy regimen. Prior hormonal therapy will **not** count as a prior regimen.
Prior treatment with trastuzumab is allowed.
6. Eastern Cooperative Oncology Group (ECOG) performance status of 0 or 1.
7. LVEF $\geq 50\%$ on baseline screening ECHO.
8. Resolution of adverse effects of recent surgery, radiotherapy, or chemotherapy to Grade ≤ 1 prior to first study treatment (with the exception of alopecia or clinically insignificant laboratory values).
9. Patients must have measurable disease. Measurable disease is defined by RECIST (version 1.1). Measurable disease is defined as at least one lesion that can be accurately measured in at least one dimension (longest diameter to be recorded). Each non-nodal lesion must be ≥ 10 mm when measured by CT, MRI or caliper measurement by clinical exam; or ≥ 20 mm when measured by chest x-ray. Lymph nodes must be ≥ 15 mm in short axis when measured by CT or MRI.
10. No active infection requiring antibiotics (with the exception of uncomplicated urinary tract infection).
11. All patients must consent to mandatory pre-treatment and post-treatment core needle biopsies.
12. Patients must have adequate hematological, liver, cardiac and kidney function within 14 days prior to first treatment:

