All patients will have their tumors molecularly profiled using the MSK-IMPACT platform, to evaluate for genomic alterations defined by MSK-IMPACT. Testing will (looking for presence/absence of genes at baseline and at end of study) be correlated to objective responses outcomes (binary covariates of CR or PR versus not) in an exploratory manner. Chi square or Fishers' exact test will be used to test this association. A subset analysis of patients who respond and then progress and have post progression material for molecular profiling will be performed in order to determine the mechanism(s) underlying acquired resistance. Specifically, we will be looking for presence of genetic alterations (at progression compared to baseline) which based on their understood biological mechanism may explain

acquired resistance. This analysis will be descriptive with the intention of understanding genetic alterations over time (at progression) and the types of mutation alterations among patients who respond and then progress. Patients will be followed up for a minimum of 12 months. Most variables above are binary (presence/absence) or expressed (yes/no) and they will be tested for association with response (yes/no) using Chi square or Fishers' exact test.

Serial pre- and post-treatment blood samples will be collected for cell-free tumor DNA analysis and sequenced using continuous quantitative methods (digital droplet PCR or hybridization capture next-generation sequencing) for the Rb, CD-K, PI3K- pathway alterations identified by pre-treatment and post-treatment tumor testing and descriptively correlated to clinical outcome. Binary covariates (presence/absence) will be tested for association with response (binary: CR or PR vs not) using Chi square of Fishers' exact test. Circulating tumor DNA is a continuous variable and these will be assessed descriptively for changes over time as part of exploratory aims.

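### Entry by any of three HER2 routes distorts one-marker-at-a-time ORR comparisons for IHC 3+ and NGS amplification; a joint marker table should replace them

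*Combined protocol and SAP*

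**What the plan says.** **Entry.** Section 6.1, criterion 2, states that "HER2 overexpression is defined as 3+ by IHC or 2+ with gene amplification by FISH" (HER2/CEP17 ratio of at least 2), or as amplification on MSK-IMPACT (fold change of at least 2). Sections 4.1 and 9.0 repeat the three routes. Criterion 1 does not require MSK-IMPACT results before treatment "unless patients do not have other test results by IHC or FISH confirming HER2 overexpression", so NGS can be the sole qualifying test. FISH counts only together with IHC 2+.

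**Planned analyses.** Section 10.0, Exploratory Correlative Studies, item 7, plans "To examine ORR in each cohort by different types of molecular alterations", with amplification taken "by NGS and ISH separately), mutation and *HER2* overexpression, and assess their predictive value for response". Exploratory objective 3 in Section 2.0 adds the aim to "assess genomic changes with response for potential predictive signatures". Exploratory objective 2 and Section 10.0, item 2, also relate the HER2 markers to one another.

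**Method.** For binary variables, Section 14.1 says "they will be tested for association with response (yes/no", by chi-square or Fisher's exact test. It calls the correlation with response exploratory. Nothing in the document mentions selection by the entry rule, a joint or stratified marker analysis, or a limit on interpretation.

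**The concern.** A patient without NGS amplification can qualify only as IHC 3+ or as IHC 2+/FISH-amplified. A patient below IHC 3+ can qualify only through amplification. So for these two markers the negative group is not HER2-negative: the entry rule has made it positive on something else. A table of ORR by one marker then compares that marker with a different HER2 marker, which does not answer the stated question of predictive value. The same selection removes most of the both-negative cell from the IHC-by-NGS table and distorts the association between the two tests.

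This is a bias and not only imprecision. Wide intervals from about 25 patients do not tell a reader that the comparison group was selected on another HER2 marker.

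Separately, exploratory objective 3 and Section 10.0, item 7, refer to cohorts, but the trial has a single arm.

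**Working it through.** **The plan's own figure.** The only design figure is the Simon rule in Section 14.1: at least 2/16 to continue, at least 5/25 to succeed, rates of 10% and 30%. Exact calculation gives type I error 0.0951 and power 0.9030, so the stated 10% and 90% hold. The marker analyses do not touch this rule, and the plan gives no figure for them. All inputs below are assumptions, because the document gives no concordance data for the three tests.

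**1. Effect on ORR, two markers.** Let marker A add *a* points to ORR and marker B add *b* points, without interaction. Let *c* be the share of enrolled A-positives who are also B-positive. If every enrolled A-negative is B-positive:

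- ORR in A-positives = base + a + c·b
- ORR in A-negatives = base + b
- crude difference = a − (1 − c)·b

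With b > 0, this is below *a* whenever c < 1, zero at b = a/(1 − c), and negative beyond that. With a = 10:

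| c | b | Crude difference (points) |
|---|---|---|
| 0.5 | 10 | 10 − 5 = +5 |
| 0.5 | 20 | 10 − 10 = 0 |
| 0.5 | 30 | 10 − 15 = −5 |
| 0.9 | 30 | 10 − 3 = +7 |

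In the third row, with a base of 5%, the crude ORRs are 5 + 10 + 15 = 30% and 5 + 30 = 35%. Within B-positives they are 45% and 35%, which recovers +10.

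**2. The actual three-route rule.** This was simulated with 4 million patients and correlated normal test scores. Assumed positive rates: IHC 3+ 20%, IHC 2+ 12%, FISH 25%, NGS 25%. Three levels of test reliability were used.

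| ORR effects in points (IHC 3+, FISH, NGS) | Reliability | IHC 3+ ORR difference, unselected | IHC 3+ ORR difference, enrolled |
|---|---|---|---|
| 5, 5, 25 | 0.5 | +14.8 | −3.8 |
| 5, 5, 25 | 0.7 | +19.9 | +0.5 |
| 5, 5, 25 | 0.9 | +27.1 | +7.0 |
| 10, 10, 10 | 0.7 | +19.9 | +9.3 |

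In the last setting NGS goes from +18.9 to +7.8 and FISH from +18.9 to +11.6, so FISH is less affected. The unselected difference also carries the other markers' effects, so it is not itself the marker's own effect.

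**3. Association between IHC 3+ and NGS.** In the same simulation, phi moves from +0.30 to −0.39 (reliability 0.5), from +0.46 to −0.23 (0.7) and from +0.68 to +0.04 (0.9).

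A hand example shows why. Per 100 screened, take 15 with both, 5 with IHC 3+ only, 5 amplified only and 75 with neither. The odds ratio is 15 × 75/(5 × 5) = 45. If *f* of the last group enrol, it becomes 15f/25. For f = 0 to 2 (IHC 2+/FISH-amplified but not NGS-amplified) that is 0 to 1.2.

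**4. Precision.** Comparing 8 patients at 45% with 10 at 35% by Fisher's exact test (two-sided 5%) has power of about 4%.

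**The case against.** A reader might infer that the planned tables will show a useful marker as useless or harmful. The document does not support that. Reversal needs the other marker to be stronger by a factor above 1/(1 − c), or one test to be much noisier than the others. With equal effects the simulation shows attenuation only. Section 3.0 calls IHC 3+ a validated surrogate for amplification, and if the tests agree closely, reversal of ORR is unlikely. Against this, Section 3.0 also reports significant IHC heterogeneity in 53% of HER2-overexpressing uterine serous tumours, so disagreement is plausible. Even at reliability 0.9 the IHC-NGS association nearly vanishes.

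A second objection is that research testing uses new biopsies, while entry may rest on any earlier result. Some patients may then be negative on every research test. This stands in part. If only a share *g* of A-negatives is B-positive, the crude difference becomes a + (c − g)·b. With a = 10, b = 30, c = 0.5 and g = 0.8 it is +1 instead of −5. In the hand example, f = 5 gives an odds ratio of 3.0. The distortion is softened but remains while *g* exceeds *c*.

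Third, Section 14.1 does not name IHC or ISH in its testing paragraph and plans no marker-to-marker test, and the analyses are exploratory with no decision rule. That is correct and limits the consequence. The stated aim is nevertheless predictive value, and no joint analysis is planned. Any claim that these tables would misdirect HER2 selection in a later trial is speculation.

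**Conclusion.** The concern holds in a limited form. For IHC 3+ and NGS amplification, marginal ORR comparisons among enrolled patients are attenuated when the tests disagree. They can reach zero or reverse when the other marker is much stronger. The IHC-NGS association is distorted even at high concordance. FISH is less affected because it qualifies only with IHC 2+. HER2 mutation is not an entry route, so its comparison is not directly affected.

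The direction follows from the entry rule; the sizes rest on assumed prevalences, reliabilities and additive effects. Marginal ORRs remain valid descriptions of the enrolled population. The fault lies in reading them as predictive value. This is a minor, inexpensive improvement to an exploratory analysis, and the primary ORR test is unaffected.

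**What to change.** In Sections 10.0 and 14.1, for the markers that define entry:

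- Make the main exploratory display ORR (n/N, exact 90% CI) in a joint table of IHC category (3+, 2+, 0-1+) by NGS amplification (yes/no), with the ISH result shown within IHC category.
- Base it on the specimen that qualified the patient. Show new-biopsy results separately, including any all-negative cell.
- Read amplification within IHC 3+. State that marginal ORRs describe the enrolled population and are not predictive value.
- Report concordance only as amplified among IHC 3+ and IHC 3+ among amplified, limited to patients with both tests. State which test qualified each patient and that selective testing can still distort the result. In the hand example, if half of the candidates had IHC only and half NGS only before entry, amplified among IHC 3+ would be 15/(15 + 2.5) = 86% instead of 15/20 = 75%.

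Keep Fisher's exact tests for alterations not used for entry. Delete *in each cohort* from exploratory objective 3 and Section 10.0, item 7.

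The cost is wording, using tests already planned or done. The downside is sparse cells: the exact 90% CI for 2/5 is 8% to 81%. The table can only be descriptive.
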